4.2. Participant Exclusion Criteria

An individual who meets any of the following criteria will be excluded from participation in this study:

1. Subjects with significant intercurrent illnesses per physician discretion
2. Subjects with active or acute infections or active peptic ulcers, unless these conditions are adequately corrected or controlled, in the opinion of the treating physician
3. Subjects with a diagnosed auto-immune disease (exceptions: subjects with controlled diabetes mellitus type I, thyroid disease, rheumatoid arthritis, vitiligo and alopecia areata not requiring treatment with immunosuppressants are eligible)
 - Subjects with a history of diabetes mellitus requiring systemic therapy within the past 3 months (i.e. either oral hypoglycemic agents or insulin) must have a documented Hemoglobin A1c $< 8.0\%$ within 90 days of registration.
4. Subjects with known genetic conditions causing pre-disposition to RT toxicity (i.e.: Li-Fraumeni, ATM deficiency, active scleroderma, etc.)
5. Subjects with a prior diagnosis of CVA or transient ischemic attack (TIA)
6. Pregnant or breastfeeding (NOTE: breast milk cannot be stored for future use while the mother is being treated on study)
7. Known additional malignancy that is active and/or progressive requiring treatment; exceptions include basal cell or squamous cell skin cancer, in situ cervical or bladder cancer, or other cancer for which the subject has been disease-free for at least three years prior to enrollment
8. Prolonged Fridericia's corrected QT interval (QTcF) > 450 ms for men and > 470 ms for women at time of enrollment
9. Subjects with symptoms of ischemic cardiac disease, congestive heart failure, or myocardial infarction within 6 months of registration and/or uncontrolled cardiac rhythm disturbance
10. Subjects with a pulmonary embolism, deep vein thrombosis, or prior clinically significant venous or non-CVA/TIA arterial thromboembolic event (e.g., internal jugular vein thrombosis) within 3 months prior to enrollment
 - Patients with a history of a venous or arterial thromboembolic event must be asymptomatic prior to enrollment and must be receiving a stable regimen of

therapeutic anticoagulation (low molecular weight heparin [LMWH] or direct oral anticoagulation [DOAC]). Use of coumadin is permitted; however, therapeutic dosing should target a specific international normalized ratio (INR) stable for at least 4 weeks prior to enrollment. NKTR-214 has the potential to down-regulate metabolizing enzymes for coumadin for approximately 1 week after administration of each dose of NKTR-214. Due to the possibility of drug-drug interactions between coumadin and NKTR-214, frequent monitoring of INR and ongoing consideration of dose adjustments are warranted throughout the patient's participation on study.

11. Subjects with significant psychiatric disabilities or seizure disorders if considered unsafe in the opinion of the treating physician
12. Subjects with symptomatic pleural effusions or ascites
13. Subjects with organ allografts
14. Subjects who require, or are likely to require, systemic treatment doses of corticosteroids, or other immunosuppressive drugs, or have used them within 2 weeks of registration (clarification: subjects receiving physiologic maintenance or replacement doses of systemic steroids or inhaled steroids are eligible)
15. Subjects with known human immunodeficiency virus (HIV) infection, active or chronic hepatitis B or hepatitis C infection, or with clinical evidence of hepatitis
16. Subjects with known hypersensitivity to IL2 or those who experienced significant immune-related AEs requiring treatment with steroids or other immunosuppressant therapy during prior treatment with ipilimumab, or anti- PD-1/PD-L1 checkpoint blockade therapy
17. Subjects who cannot provide independent, legal, informed consent

4.3. Strategies for Recruitment and Retention

The methods used for recruitment of subjects in the study will be devoid of any procedures that may be construed as coercive. The recruitment process will not involve any restrictions on socio-demographic factors, including gender or ethnic characteristics, of the subject population. However, the composition of the study participant population will depend on patient sources available to the clinical site.

The trial will be managed by physicians at the University of Wisconsin Hospital and Clinics and will be conducted at the University of Wisconsin Hospital and Clinics. 24 eligible subjects will be recruited from the treating physicians' own clinical practice, through clinic contacts, and referring physicians.

4.4. Treatment Assignment Procedures

Patients who agree to participate in the clinical trial and have been deemed eligible to do so based upon inclusion/exclusion criteria will be enrolled after they provide written informed consent. The study coordinator will assign a case number and register the patient in the UWCCC OnCore database prior to study therapy. The following information will be recorded for the purpose of registration.

- Protocol number
- Subject's name
- Subject's medical record number
- Subject's demographic data such as:

- Birth date
- Race
- Ethnicity
- Gender
- Insurance type
- Date of consent

4.5. Participant Withdrawal or Discontinuation from Study Procedures/Intervention

4.5.1. Reasons for Participant Withdrawal or Discontinuation from Study Procedures/Intervention

Subjects are free to withdraw from participation in the study at any time upon request.

Treatment may continue as specified in the above treatment modality sections or until one of the following criteria applies:

- disease progression;
- intercurrent illness that prevents further administration of treatment;
- unacceptable adverse event(s) (as determined by the subject or treating physician)
- subject decides to withdraw consent for participation in the study;
- subject refuses further treatment (without withdrawing consent for study participation);
- general or specific changes in the subject's condition render the subject unacceptable for further treatment in the judgment of the treating physician;
- new data related to the experimental agent which would suggest that continuing treatment on protocol would impose unwarranted potential risks beyond what was known at the time of treatment initiation;
- delay of any protocol therapy for > 15 weeks
- a female subject becomes pregnant;

Subjects will be removed from protocol therapy and the site investigator notified when any of the criteria listed above apply. The reason for discontinuation of protocol therapy will be documented on the electronic case report form (eCRF).

4.5.2. Handling of Participant Withdrawals from Study or Participant Discontinuation of Study Intervention

Subjects will be removed from protocol therapy and the site investigator notified when any of the criteria listed above apply. The reason for discontinuation of protocol therapy will be documented on the eCRF.

If a subject decides to withdraw from the study (and not just from protocol therapy) all efforts should be made to complete the final study assessments. The study team will attempt to contact the subject by telephone or through a clinic visit to determine the reason for the study withdrawal. If the reason for withdrawal is an adverse event, it will be recorded on the eCRF. The study team will make all efforts to undertake protocol-specified safety follow-up procedures to capture AEs, serious adverse events (SAEs), and unanticipated problems (UPs).

If a subject leaves the study prior to administration of NKTR-214, they will be replaced by an additional subject.

4.6. Premature Termination or Suspension of Study

This study may be suspended or prematurely terminated if there is sufficient reasonable cause. Written notification, documenting the reason for study suspension or termination, will be provided by the suspending or terminating party to the UWCCC DSMC and regulatory authorities. The principal investigator will also promptly inform the institutional review board (IRB) and will provide the reason(s) for the termination or suspension.

Circumstances that may warrant termination include, but are not limited to:

- Determination of unexpected, significant, or unacceptable risk to participants
- Insufficient adherence to protocol requirements
- Poor enrollment (< 1 patient in any 18 month period)
- Request to discontinue the study from a regulatory authority
- Company business decision
- Data that are not sufficiently complete and/or evaluable

5. STUDY INTERVENTION

5.1. Pembrolizumab (Standard of Care)

5.1.1. Acquisition

Pembrolizumab is kept on formulary and would be administered as part of the standard of care for participants enrolled on this study.

5.1.2. Formulation, Packaging, Labeling, and Administration

Commercial supplies will be utilized. Formulation and labeling will be per package inserts. UW Health standard operating procedures will be followed for administration.

5.2. NKTR-214 (Research-related)

The study will utilize the UWCCC's Pharmaceutical Research Center (PRC). The PRC ensures that drug research protocols proceed optimally through UWCCC's established medication use system and in accordance with all federal, state, institutional and sponsor regulations governing clinical research.

5.2.1. Acquisition

NKTR-214 will be provided by Nektar Therapeutic's designated manufacturer and an estimated 3-4 month supply will be delivered directly to the institution based on anticipated rates of accrual.

5.2.2. Formulation, Packaging, and Labeling

NKTR-214 drug product is packaged as a sterile, single-use, lyophilized powder in 5 mL glass vials to be reconstituted and diluted for IV injection. Each vial of NKTR-214 drug product has a label claim of 1.0 mg rhIL2.

5.2.3. Product Storage and Stability

The product will be stored at -20 °C +/- 5 °C. Vials will be protected from light prior to reconstitution. After reconstitution, the solution does not need to be protected from light. The solution may be held at room temperature for up to 6 hours prior to infusion.

5.2.4. Dosage, Preparation and Administration of Study Product

NKTR-214 will be reconstituted in 1.1 mL water for injection by the PRC. The reason for reconstitution in 1.1 mL is a 0.1 mg overflow (total of 1.1 mg per vial) to ensure the full 1 mg of medication can be withdrawn for injection. The product should not be shaken to reconstitute but can be gently inverted. It should subsequently be diluted into 5 % dextrose or 0.9 % sodium chloride, USP. The final concentration for infusion should be 0.0024 mg/mL to 0.0675 mg/mL.

PRC will document release of NKTR-214 to research nurse/staff or physician. Each subject will receive NKTR-214 through a freely-running peripheral IV catheter in the D5W or NS as noted above. Dosage will be 0.006 mg/kg and can be decreased to 0.003 mg/kg for some participants according to rules in section 5.5 of this protocol. **AN IN-LINE FILTER INCLUDING IN-LINE FILTER EXTENSION SETS MUST NOT BE USED DUE TO DRUG LOSSES ON THE FILTER MEMBRANE.** If a filter must be used, only 15 µm pore size drip-chamber filters are acceptable. NKTR-214 infusion must be promptly followed by a flush of diluent to clear the line. Care must be taken to assure sterility of the prepared solution as the product does not contain any antimicrobial preservative or bacteriostatic agent. NKTR-214 infusions prepared in 0.9 % NaCl solution or 5 % Dextrose solutions are compatible with polyvinyl chloride or polyolefin containers and infusion sets, as well as closed-system transfer devices (CSTDs) when following specific instructions to ensure prepared dose accuracy. Please refer to the Pharmacy Manual/current Investigators Brochure for requirements regarding preparation and administration.

5.2.5. Premedication for Flu-like Symptoms

These recommendations have been developed to reduce the risk of flu-like symptoms during the first week of each treatment cycle. Investigator may modify these recommendations based on the needs of individual patient.

- Administer acetaminophen (eg, 650 mg every 6 hours) or NSAIDs (eg, ibuprofen 400 mg every 6 hours) a minimum of 30 minutes prior to treatment on Day 1 of each cycle.
- Administer acetaminophen or NSAIDs q6h on Day 2 to 5 of each cycle.

- Instruct patients on the signs and symptoms (fever over 100.4 °F or 38 °C, chills and sweats, muscle aches or joint pain, fatigue and weakness), how to treat with acetaminophen or NSAIDs, and when to call their treating oncologist or present for medical care.

5.3. Accountability Procedures for the Study Product

A 3-4 month supply of NKTR-214 will be delivered from Nektar Therapeutics to the UWCCC Pharmaceutical Research Center (PRC) at the beginning of the study and will be replenished 3-4 times annually in an amount sufficient to meet the demands of anticipated study accrual. UWCCC PRC will maintain careful inventory of the study drug, per standard operating procedures. Any unused NKTR-214 remaining at the end of this study will be destroyed by the UWCCC PRC.

5.4. Assessment of Participant Compliance with Study Product Administration

All therapeutic medications will be administered at UW facilities via intravenous route and delivery will be documented in the UWHC electronic medical record system by research nurses or treating physicians. External beam radiation therapy delivery will be confirmed via the record and verify system.

5.5. Modification or Delay of Protocol Therapy

Participants experiencing Grade 4 toxicity with a probable or definite attribution to NKTR-214 will discontinue this treatment indefinitely. Participants experiencing Grade 4 toxicity with an unrelated, unlikely, or possible attribution to NKTR-214 will delay further therapy with this agent until this toxicity resolves to baseline or < Grade 2, or is deemed irreversible.

Participants with toxicities ≤ Grade 3 will remain eligible to continue or to resume NKTR-214, but may be required to take a treatment break according to the following rules:

Participants experiencing Grade 3 toxicity with an unrelated, unlikely, or possible attribution to NKTR-214 or Grade 2-3 toxicity with a probable or definite attribution to NKTR-214 will delay further therapy with this agent until this toxicity resolves to baseline or < Grade 2, or is deemed irreversible. In participants who experience such a toxicity, if this toxicity resolves to baseline or < Grade 2 prior to the participant's next scheduled dose of NKTR-214 then no delay of therapy is required. Participants with any Grade 1 toxicity or Grade 2 toxicity with an unrelated, unlikely, or possible attribution to NKTR-214 will continue that therapy.

Participants who experience a treatment delay due to a Grade 3 toxicity with a possible, probable, or definite attribution to NKTR-214 or who experience a Grade 4 toxicity with a possible attribution to NKTR-214 will undergo a dose reduction to 0.003 mg/kg if resuming NKTR-214 dosing.

For all participants, protocol treatment may be delayed ≤ 1 week from the expected day of the next treatment for any reason. If protocol treatment is delayed > 1 week, subjects will proceed with protocol therapy once they are determined by the treating physician to be appropriate for further protocol therapy. Any dosing interruption will not impact the time interval or dose of subsequent treatment cycles for participants that remain on study. Missed doses of drug will not

be made up. Patients requiring systemic corticosteroids during a treatment break must be tapered off treatment doses of these prior to resuming protocol therapy. Patients delayed for > 15 weeks will be discontinued from protocol therapy.

Anti-PD-1 therapy and radiation therapy will be delivered and/or held per standard-of-care practice for all patients in this study, per the determination of the treating physician. Any patient for whom anti-PD-1 therapy is discontinued will also discontinue treatment with NKTR-214. Any patient for whom anti-PD-1 therapy is held will also have NKTR-214 held at least until the patient is determined by the treating physician to be eligible for anti-PD-1 therapy again, per standard-of-care practice. In that setting the above rules for discontinuing or holding NKTR-214 will still apply and a patient becoming eligible to resume anti-PD-1 therapy after a hold may resume NKTR-214 only if they also meet the above criteria for resuming NKTR-214. If NKTR-214 is held or discontinued, a patient may continue on anti-PD-1 therapy on this study if this is deemed to be within the standard-of-care for anti-PD-1 therapy administration, per the treating physician.

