For unexplained neurological symptoms (such as hemiparesis, confusion, dysarthria, or visual disturbances) that may be associated with CVA: **perform neurological imaging with MRI including diffusion-weighted imaging (DWI) as soon as feasible after initial presentation of symptoms (preferably within 24 hours)**. DWI MRI is preferred, but if contraindicated, alternative imaging modalities may be used.

If imaging is consistent with a CVA, proceed to the following:

1	
For any new CVA events confirmed by imaging (DWI MRI preferred unless contraindicated), regardless of neurological symptoms (e.g., cryptogenic CVA):
 
 • Discontinue study treatment for patients receiving NKTR-214 in combination with a checkpoint inhibitor 
For suspected TIA without clear alternative etiology:
 
 • Study treatment for patients receiving NKTR-214 in combination with a checkpoint inhibitor may be continued only after careful risk-benefit assessment by the Investigator
2	Obtain a neurology consultation
3	Perform laboratory assessments (Assessments include coagulation studies including D-dimer, complete blood count with differential, serum blood urea nitrogen, and creatinine. Additionally, collect an exploratory biomarker test if a baseline exploratory biomarker test was collected).
4	Consider cardiac echocardiogram (trans-esophageal as appropriate) to evaluate for potential source of emboli.

CVA = cerebrovascular accident; DWI = diffusion-weighted imaging; MRI = magnetic resonance imaging; TIA = transient ischemic attack.

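### Section 5.5 keeps some patients on NKTR-214 after a stroke that Appendix B says must end study treatment, and no text says which rule governs

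*Combined protocol and SAP*

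**What the plan says.** Section 5.5 sorts toxicities by grade and by attribution to NKTR-214.

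- **Continue.** "Participants with any Grade 1 toxicity or Grade 2 toxicity with an unrelated, unlikely, or possible attribution to NKTR-214 will continue that therapy".
- **Delay.** Grade 2 judged probable or definite, any Grade 3, and Grade 4 judged unrelated, unlikely or possible are held "until this toxicity resolves to baseline or < Grade 2, or is deemed irreversible". For the Grade 2 and 3 events in this group, if the event resolves before the "next scheduled dose of NKTR-214 then no delay of therapy is required".
- **Stop.** Only Grade 4 judged probable or definite ends NKTR-214 permanently.
- **Dose.** Patients delayed for a Grade 3 event judged possible, probable or definite, and those with a Grade 4 event judged possible, "will undergo a dose reduction to 0.003 mg/kg if resuming NKTR-214 dosing".

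Appendix B deals with stroke specifically. Its first row begins "For any new CVA events confirmed by imaging (DWI MRI preferred unless contraindicated), regardless of neurological symptoms", and the action is to discontinue study treatment. Neither grade nor attribution is a condition. Only suspected transient ischemic attack (TIA) without a clear alternative cause is left to the investigator's risk-benefit judgment.

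Section 1.3.1 names Appendix B as a CVA mitigation and says the dose modification guidelines and discontinuation criteria were also updated for CVA. Section 5.5 does not mention CVA or Appendix B, and the stopping reasons in Section 4.5.1 do not list CVA. Appendix B describes itself as guidance to the investigator.

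**The concern.** For a low-grade stroke the two instructions cannot both be obeyed: one section continues the drug and the appendix ends it. Nothing in the protocol ranks one above the other.

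Staff have reason to look in Section 5.5. Section 5.2.4 and footnote 3 of the table in Section 5.7.3 send them there for dose reduction, and Section 5.7.1 sends them there for permanent discontinuation after a creatinine rise. In the body of the protocol, Appendix B is cited only in the background section on risks.

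CVA is the only adverse event of special interest (Section 8.1.4). Section 1.3.1 reports CVA in 8 of 478 patients on NKTR-214 plus nivolumab and 3 of 43 on the triplet with ipilimumab, including one fatal event, while calling the relationship to treatment unclear. At stake is re-exposure to NKTR-214 after a stroke because the dosing section was followed as written.

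**Working it through.** No sample-size or error-rate figure is involved. The check lists every combination that Section 5.5 covers and compares it with Appendix B.

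**Inputs.** Grades 1 to 4 (Grade 5 is death, so no dosing decision follows). Five attribution levels from Section 8.3.1. This gives 4 × 5 = 20 combinations.

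**Section 5.5 applied to a CVA with no exception:**

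| Grade | Unrelated | Unlikely | Possible | Probable | Definite |
|---|---|---|---|---|---|
| 1 | continue | continue | continue | continue | continue |
| 2 | continue | continue | continue | delay | delay |
| 3 | delay | delay | delay | delay | delay |
| 4 | delay | delay | delay | stop | stop |

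- Continue: 5 (Grade 1) + 3 (Grade 2) = 8.
- Delay, resumption allowed: 2 (Grade 2) + 5 (Grade 3) + 3 (Grade 4) = 10.
- Stop: 2 (Grade 4).
- Total: 8 + 10 + 2 = 20.

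**Appendix B for a new imaging-confirmed CVA:** stop in 20 of 20.

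**Comparison.** The 8 continue cells contradict Appendix B outright. The 2 stop cells agree with it as regards NKTR-214. In the 10 delay cells, holding the drug and then stopping it under Appendix B satisfies both texts, so these are a gap rather than a contradiction. Within those 10:

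- No delay is needed if the event resolves before the next dose in 2 (Grade 2 probable or definite) + 5 (Grade 3) = 7.
- No dose reduction is required on resumption, so 0.006 mg/kg stands, in 2 (Grade 2 probable or definite) + 2 (Grade 3 unrelated or unlikely) + 2 (Grade 4 unrelated or unlikely) = 6.
- The dose falls to 0.003 mg/kg in 3 (Grade 3 possible, probable or definite, and only if a delay occurred) + 1 (Grade 4 possible) = 4.

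**Sensitivity to reachable grades.** The protocol does not reproduce the CTCAE grade definitions for CVA, so which cells can occur is an assumption. Dropping Grade 1 leaves 15 combinations: 3 continue, 10 delay and 2 stop. Appendix B does expect strokes without symptoms, because its rule applies regardless of neurological symptoms.

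**Linked ambiguity.** Appendix B stops study treatment without saying whether that covers pembrolizumab. Section 5.5 says: "If NKTR-214 is held or discontinued, a patient may continue on anti-PD-1 therapy on this study", if that is within standard of care. After a CVA, a reader cannot tell whether pembrolizumab on study must also end.

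**The case against.** The strongest reply is that the protocol does contain the right rule, and that a specific CVA instruction would ordinarily prevail over a general toxicity rule. On that view this is a missing cross-reference. Appendix B is very probably the intended rule, but precedence has to be inferred: the appendix calls itself guidance, whereas Section 5.5 is worded as a requirement.

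Other safeguards exist:

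- Section 4.5.1 removes a patient for an adverse event that the patient or treating physician finds unacceptable, or when the physician judges the patient's condition unsuitable for further treatment. This reaches all 20 combinations, so Section 5.5 compels dosing only when read alone. It is still discretionary, whereas Appendix B leaves only suspected TIA to judgment.
- After a delay of more than one week, the treating physician must find the patient fit to proceed. The 8 continue cells create no delay, so this check does not reach them. Nor does "Patients delayed for > 15 weeks will be discontinued from protocol therapy".
- "Any patient for whom anti-PD-1 therapy is discontinued will also discontinue treatment with NKTR-214", and a hold of anti-PD-1 also holds NKTR-214. Both depend on the physician's anti-PD-1 decision.
- Any CVA is reported as an event of special interest, and the chair of the Data and Safety Monitoring Committee (DSMC) reviews 24-hour serious-event reports. These follow the event and do not set the next dose.

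It is also fair to say that few patients may be affected. If the doublet rate in Section 1.3.1 carried over to this trial (an assumption, since radiation is added and prior CVA or TIA is excluded), the expected number of CVAs of any grade among 24 patients is 24 × 8/478 ≈ 0.4, and the chance of at least one is 1 − (1 − 8/478)^24 ≈ 33%. Direct conflict needs the low-grade subset, whose share the protocol does not give. Rarity limits the expected harm but does not reconcile the texts. The pembrolizumab question is secondary and does not bear on the NKTR-214 conflict.

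**Conclusion.** The concern holds. Section 5.5 orders NKTR-214 to continue in 8 of 20 grade-by-attribution combinations where Appendix B ends study treatment, or in 3 of 15 if Grade 1 CVA cannot occur. In 10 more it permits a restart that Appendix B does not. Only the continue cells are direct contradictions. The counts describe rules, and how often the conflict would arise cannot be estimated from the documents. The count does not depend on which text staff would follow in practice; that the appendix was meant to govern is an inference from Section 1.3.1. Because Section 1.3.1 describes CVA updates that Sections 4.5.1 and 5.5 do not contain, this is an error in the operative text and should be corrected.

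**What to change.** Add one sentence to each of Sections 5.5 and 4.5.1: any new imaging-confirmed CVA, whatever its grade or attribution, permanently discontinues study treatment under Appendix B, which overrides the grade-based rules. Keep the TIA exception: suspected TIA without a clear alternative cause may continue only after the risk-benefit assessment in Appendix B. State whether study treatment in Appendix B includes pembrolizumab. With this change, all 20 combinations read stop for a confirmed CVA, against 2 now for NKTR-214. The cost is a short text amendment, with no effect on endpoints, analysis or sample size.
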